possible that adolescents seeking treatment from a community clinic might be at a greater risk for clinical deterioration and might be less likely to demonstrate a clinical improvement than if they received the treatments provided in this study. What is experimental in this study is the criteria for initiating a change in the treatment plan, the timing of a potential change in the treatment plan, and the type of change to the treatment plan. Currently, there are virtually no empirically-derived guidelines to direct clinicians in deciding whether, when, or how to alter a treatment plan for adolescent depression. Consequently, we expect the relation of the anticipated benefits to the risks to be at least as favorable to the subjects as that presented by available non-study treatment.

2 Study Objectives

Aim 1: Assess the feasibility and acceptability of the personalized continuation treatment strategy.

- Hypothesis 1: Adolescents who responded to the acute phase treatment provided in the K23 study and their parents will consent to participate in continuation treatment.
- Hypothesis 2: Adolescents will be adherent to continuation treatment and will complete the continuation treatment protocol.
- Hypothesis 3: Adolescents and parents will report satisfaction with continuation treatment.
- Hypothesis 4: Treating clinicians will report satisfaction with continuation treatment.

Aim 2: Estimate variances of primary and secondary outcomes with the continuation treatment.

- Hypothesis 5: Adolescents who were responders to acute treatment will show sustained response to continuation treatment.
- Hypothesis 6: Adolescents who were partial responders to acute treatment will show significant improvement in depressive symptoms and social and global functioning.

Aim 3: Conduct exploratory hypothesis-generating analyses to inform further development of the personalized continuation treatment strategy to be tested in a subsequent R01 proposal.

3 Study Design

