3.1 General Design

Adolescents will receive 16 weeks of continuation treatment. They will be treated by the same clinicians who provided their acute phase treatment. The personalized continuation treatment plan is illustrated below.

Continuation IPT-A. The goal of IPT-A²⁰ is to decrease depressive symptoms by focusing on current interpersonal difficulties and helping the individual improve his or her relationships and interpersonal interactions. This is accomplished through review of the

[figure not shown]
[figure not shown]
adolescent's significant relationships which leads to the identification of the interpersonal problem areas on which to focus the treatment, development of communication and interpersonal problem solving skills, and role-playing. During the Continuation IPT-A sessions, the therapist will continue to emphasize the interpersonal strategies that were learned and practiced during the acute phase, and address any current interpersonal problems before they result in a recurrence of depressive symptoms. Adolescents who have responded to acute phase treatment (CGI-I = much improved or very much improved) will attend 4 biweekly IPT-A sessions followed by 2 monthly sessions. Adolescents who showed a partial response to acute phase treatment (CGI-I = minimally improved) will attend 8 weekly IPT-A sessions followed by 2 monthly sessions.

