Continuation Pharmacotherapy. Adolescents who received fluoxetine during the acute phase and were responders (CGI-I = much improved or very much improved) will continue their acute phase dosing regimen and will meet with the psychiatrist on a monthly basis. Adolescents who received fluoxetine during the acute phase and were partial responders (CGI-I = minimally improved) will enter the continuation phase on 40mg fluoxetine, and will have their dose increased to 60mg.⁴⁰ Partial responders will meet with the psychiatrist biweekly for the first 2 months and monthly for the second 2 months. Adolescents who received only IPT-A during acute phase and were partial responders (CGI-I = minimally improved) will begin treatment with fluoxetine during the continuation phase, in addition to continuing their IPT-A treatment. The dosage schedule will be 10mg per day for the first week and 20mg per day for the following 5 weeks. If no treatment response is observed by the 6th week, the dosage can be increased to 40mg per day.⁴¹ Pharmacotherapy sessions will be scheduled weekly for the first 4 weeks and biweekly thereafter. Pharmacotherapy sessions will include assessment of vital signs, adverse effects, safety, and symptomatic response.

Assessments. Assessments will be administered by independent evaluators who are blind to treatment condition. Adolescents will enter continuation treatment at week 16. Assessments will be conducted at week 24 and 32. The week 32 evaluation is already funded through the K23 study. Assessment measures include the Schedule for Affective Disorders and Schizophrenia for School-aged Children-Present and Lifetime Version (K-SADS-PL),⁴² Children's Depression Rating Scale-Revised (CDRS-R),⁴³ Columbia Suicide Severity Rating Scale (CSSRS),⁴⁴ Global Assessment Scale for Children (C-GAS),⁴⁵ Beck Depression Inventory-II (BDI-II),⁴⁶ Social Adjustment Scale-Self-report (SAS-SR),⁴⁷ Conflict Behavior Questionnaire (CBQ),⁴⁸ and Client Satisfaction Questionnaire (CSQ-8).⁴⁹

CONFIDENTIAL

Treatment Phase	Acute	Continuation	
Assessment	Week 16	Week 24	Week 32

R = Responder (CGI-I = much improved or very much improved), PR = Partial Responder (CGI-I = minimally improved), NR = Nonresponder (CGI-I = no change or worsening)

CONFIDENTIAL

This material is the property of the University of Minnesota. Do not disclose or use except as authorized in writing by the study sponsor

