4.3 Subject Recruitment and Screening

We will only enroll adolescents who completed acute phase treatment in our linked study ([name], PI, K23MH090216) and showed at least a partial response to treatment (CGI-I of minimally improved or better ($CGI-I \leq 3$)). Adolescents will enter continuation treatment having either received 12 sessions of IPT-A, 16 sessions of IPT-A, or 12 sessions of IPT-A plus fluoxetine.

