7.1 Sample Size Determination

Statistical experts warn against over-interpreting pilot data for estimating power and effect sizes for larger clinical trials.⁵¹ Consequently, the proposed research study does not aim to evaluate the efficacy of the adaptive treatment strategies. Rather, the sample size was determined by the study aims which are to demonstrate the feasibility and acceptability of implementing the adaptive treatment strategies. With these aims in mind, an intent-to-treat sample size of 30 was selected. A sample size of 30 will help ensure there are enough depressed adolescents in each adaptive treatment strategy to assess feasibility and acceptability.

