- Hypotheses 5 & 6: (1) Primary analyses will examine within-subject change scores in CDRS, C-SSRS and CGAS over the course of acute and continuation treatment using repeated measures analysis of variance (ANOVA). Linear regression and analysis of covariance (ANCOVA) adjusting for pre-treatment scores will also be used to analyze changes in adolescents' outcomes. The magnitudes of changes in outcomes variables over time will be assessed using the paired t-test or Wilcoxon signed-rank test for continuous variables. Mixed-effects regression models will also be employed to compare CDRS, C-SSRS, and CGAS scores over multiple time points in order to obtain information on specific patterns of change over time. (2) Secondary analyses comparing within-subjects change scores across treatment groups on self-report measures of depression (BDI-II) and functioning (CBQ, SAS-SR) will be conducted using two-sample t-test, Wilcoxon rank sum test, and linear regression analysis. Hierarchical linear modeling (HLM) will also be conducted to compare scores over multiple time points within each treatment group. (3) Recovery will be defined as an absence of depression symptoms on the KSADS-PL for at least 8 weeks. Relapse will be defined as the reemergence of 5 or more symptoms of depression on the KSADS-PL. The percentage of adolescents who meet recovery criteria, and associated 95% confidence interval will be calculated. The percentage of adolescents who meet relapse criteria, and associated 95% confidence interval will be calculated. For those with a relapse, the mean (SD) time from recovery to relapse will be calculated.

Exploratory Analyses: Exploratory analyses will be conducted to determine whether comorbid psychiatric disorders, baseline severity of depression, and different forms of functioning (CBQ, SAS-SR, CGAS) predict or moderate positive or negative treatment outcomes. Potential predictors and moderators will be used to refine the personalized treatment strategy that will be tested in the subsequent R01.

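### The primary analysis for Hypotheses 5 and 6 is measured from the start of acute treatment, so it does not isolate change during continuation treatment

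*Combined protocol and SAP*

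**What the plan says.** Section 2 gives Aim 2 as "Estimate variances of primary and secondary outcomes with the continuation treatment". Under it, Hypothesis 5 is "Adolescents who were responders to acute treatment will show sustained response to continuation treatment" and Hypothesis 6 is "Adolescents who were partial responders to acute treatment will show significant improvement in depressive symptoms and social and global functioning".

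Section 3.1 sets the timing: "Adolescents will receive 16 weeks of continuation treatment", and "Adolescents will enter continuation treatment at week 16. Assessments will be conducted at week 24 and 32". Its schedule table also shows an assessment at week 16.

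Section 4.3 enrols only completers of the linked acute study who "showed at least a partial response to treatment (CGI-I of minimally improved or better", that is, CGI-I of 3 or less. Section 4.2 excludes CGI-I of 4 or more.

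Section 7.2, item (1) for Hypotheses 5 and 6, reads: "Primary analyses will examine within-subject change scores in CDRS, C-SSRS and CGAS over the course of acute and continuation treatment", by repeated measures ANOVA. The same item adds regression and ANCOVA on an undefined pre-treatment score, paired t or signed-rank tests, and mixed models over several time points. Item (3) adds recovery and relapse percentages with 95% CI. None of these names week 16.

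Section 3.2 makes feasibility and acceptability the primary outcome. Section 7.1 says "the proposed research study does not aim to evaluate the efficacy of the adaptive treatment strategies".

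**The concern.** The question asked and the interval analysed do not match. Hypothesis 5 asks whether a response present at week 16 is kept. Hypothesis 6 asks whether adolescents who had improved only minimally by week 16 improve further. The stated primary window opens at the start of acute treatment, so it includes improvement that was a condition of entry. A significant time effect over that window is close to built in and says little about weeks 16 to 32.

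At stake are the reading of Hypotheses 5 and 6 and the variances that Aim 2 is meant to supply. Section 2 says that this work leads to a later grant proposal, so a change score on the wrong interval could be carried forward.

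**Working it through.** **Inputs.** From the documents: entry rule CGI-I of 3 or less; continuation entry at week 16; assessments at weeks 24 and 32; N = 30; and relapse of 25-50% after acute treatment in the studies summarised in section 1.1, used here only as a benchmark. The documents give no SD, correlation, effect size or alpha for these outcomes, so there is no planned figure to reproduce. Everything else below is assumed. Scores are in SD units and lower is better.

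**1. Mean change if some responders relapse.** Let responders have mean acute change −D, and let a fraction p lose all of it by week 32, regardless of its size.
- From acute start: −(1 − p)D. With p = 0.5 this is −0.5D, still an improvement.
- From week 16: +pD. With p = 0.5 this is +0.5D, a worsening.

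**2. Rejection with zero continuation change, first model.** Assumed: reliability 0.8; entry if the observed score improved by week 16; SD of true acute change 0.7 times the true-score SD; n = 30; visits at acute start and weeks 16, 24 and 32; Greenhouse-Geisser correction; 1,500 trials per row; two-sided 5%.

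| Mean acute improvement before selection | ANOVA, all four visits | Mean change, start to week 32 | Paired t, week 16 to 32 | Mean change, week 16 to 32 |
|---|---|---|---|---|
| 0 | 100% | −0.54 | 33% | +0.18 |
| 0.5 | 100% | −0.82 | 14% | +0.10 |
| 1.0 | 100% | −1.16 | 7% | +0.06 |
| 1.5 | 100% | −1.57 | 5% | +0.02 |

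Now add a true continuation worsening of 0.5 after a mean acute improvement of 1.0. Change from acute start is −1.16 + 0.50 = −0.66, a significant improvement in 99% of trials. The week 16 to 32 contrast averages +0.56 and rejects in 99.5%.

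**3. The same question, second model.** CGI-I is a separate rating, correlated 0.5 to 0.9 with acute change, with error either shared with the outcome or independent of it. Central inputs: acute-change SD 0.8, noise SD 0.4, 35% partial responders, mean acute change 0 to −1. Wide inputs: acute-change SD 0.5 to 1.0, noise SD 0.4 to 0.7, 20% to 50% partial responders. There were 2,000 trials per setting.
- Pooled n = 30, zero continuation change, all four visits: rejects in 64-100% (central) and 20-100% (wide). The 20% needs no mean acute change, correlation 0.5, noise SD 0.7 and independent error. With mean acute change of at least 0.5 it is 93-100% (wide).
- Weeks 16, 24 and 32 only: 3-6% under independent error; 6-27% (central) or 5-56% (wide) under shared error.
- 20 responders, 50% relapse against none: the acute-inclusive rejection rate falls by 0 to 12 points (central). Detection of worsening from week 16 rises from 2-3% to 24-92% (independent error) or from 7-29% to 35-97% (shared error).
- 10 partial responders: the rates run from 4% to 98%, too wide to support a claim for Hypothesis 6.

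C-SSRS was not modelled.

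**4. Variance for Aim 2.** In responders, let v and m be the variance and mean of acute change, s the noise SD, p the fraction losing the gain, with independent error. Then

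Var(start to 32) / Var(16 to 32) = [(1 − p)v + p(1 − p)m² + 2s²] / [pv + p(1 − p)m² + 2s²].

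- p = 0, before selection: v = 0.8² = 0.64 and 2s² = 2 × 0.4² = 0.32, so the ratio is 0.96/0.32 = 3.0. Selecting responders shrinks v; the simulated ratio is about 1.8-2.7.
- p = 0.25: simulated ratio 1.2-1.5.
- p = 0.5: numerator and denominator are identical, so the ratio is 1.0. The simulation agrees.

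**5. Precision after re-anchoring.** Half-width = t × SD of difference / √n. For an assumed week 16-to-32 correlation of 0.84 down to 0.3, SD of difference = √[2(1 − r)] = 0.57 to 1.18.
- n = 10 (t = 2.262): about ±0.40 to ±0.85 SD.
- n = 20 (t = 2.093): about ±0.26 to ±0.55 SD.
- Sustained response in 16 of 20, exact 95% CI: 56% to 94%.

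**The case against.** The strongest reply is that this is an uncontrolled feasibility pilot that disclaims efficacy evaluation, and that 7.2 already contains tools that reach continuation change. Paired tests can be run from week 16, mixed models can show the pattern over visits, and the relapse percentage speaks directly to a lost response. Pre-treatment could mean week 16, since this study's treatment is the continuation phase. Hypotheses 5 and 6 name their own populations, so a split by response group is implied, and the pooled n = 30 rate matches neither hypothesis. An acute-start reference also has a proper role in Hypothesis 5, because response was earned against it.

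Much of this stands, and it limits the point. A reader might infer that the plan cannot tell a kept response from a lost one. The documents do not support that: the small fall in rejection rate in step 3 concerns only the overall time effect, and item (3) measures relapse. A reader might also infer that the plan pools the two groups; it only fails to state the split in item (1). Nor can it be said that Aim 2's variance is inflated by a fixed factor, because step 4 shows the ratio falling to 1.0 as relapse rises to 50%.

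The stated primary window survives the reply. None of the other analyses is tied to week 16, so the continuation contrast would be chosen after the data are seen. Reading pre-treatment as week 16 would settle the ANCOVA covariate but not the window.

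**Conclusion.** The point holds, as something that should be fixed for the secondary aims. The mismatch between the hypotheses and the primary window follows from the text alone. Its numerical size rests entirely on assumed inputs: with no continuation change, the pooled acute-inclusive test rejects in most trials under central inputs, with one weak corner at 20%. The relapse arithmetic in step 1 needs only that loss of gain is unrelated to its size. No magnitude is claimed for Hypothesis 6, and no single variance multiplier should be quoted for Aim 2.

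It would be tempting to conclude that the trial's main result is compromised. It is not: the feasibility and acceptability endpoint does not use these change scores, and section 7.1 sets efficacy evaluation aside.

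Moving the baseline to week 16 does not turn the estimate into a treatment effect. There is no control group, and if CGI-I shares error with the outcome, selection at week 16 alone can produce apparent worsening.

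**What to change.** In section 7.2:

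1. For the score outcomes in Hypotheses 5 and 6, name week 16 as baseline and define pre-treatment as week 16. Make week 16 to 32, with week 24, the primary window. Report acute-phase change separately, as descriptive.
2. With the models already planned, report week 16-to-32 change with its SD (for Aim 2) and 95% CI, separately for acute responders (Hypothesis 5) and partial responders (Hypothesis 6).
3. For Hypothesis 5, report the relapse percentage among week 16 responders with 95% CI. Beside it, give the proportion still rated CGI-I 1 or 2 at weeks 24 and 32. State that this CGI-I keeps its acute-start reference; re-anchored to week 16, an unchanged responder would score 4 and count as a non-responder. State also whether the rating is the therapist's, which section 8.4 has made at each therapy session, or the blinded evaluator's.
4. State that the estimates are uncontrolled and may include regression to the mean from selection at week 16.

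As a separate matter, reconcile the Study Summary with 7.2. The Summary lists SAS-SR where 7.2 lists C-SSRS, and it uses early and late decision point groups that 7.2 does not mention.

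The cost is almost all wording, since the visits are already in the schedule. Item 3 depends on a CGI-I rating being available at or near weeks 24 and 32. The real price is in the results: smaller, less favourable changes, with intervals as wide as those in step 5.

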3.4 Primary Safety Endpoints

Primary safety endpoints include suicidality (Columbia Suicide Severity Rating Scale), side effects (Side Effects Measure), and vital signs (blood pressure, pulse, weight).

4 Subject Selection and Withdrawal

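### The primary suicidality endpoint is analysed only as net change in C-SSRS scores, which can hide new or worse suicidality in a few adolescents

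*Combined protocol and SAP*

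**What the plan says.** Section 3.4: "Primary safety endpoints include suicidality (Columbia Suicide Severity Rating Scale), side effects (Side Effects Measure), and vital signs (blood pressure, pulse, weight".

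Section 7.2, Hypotheses 5 & 6, item (1), is the only part of the statistical plan that names the C-SSRS. It does so twice: "Primary analyses will examine within-subject change scores in CDRS, C-SSRS and CGAS over the course of acute and continuation treatment" (repeated measures ANOVA), and "Mixed-effects regression models will also be employed to compare CDRS, C-SSRS, and CGAS scores over multiple time points". The same item adds "Linear regression and analysis of covariance (ANCOVA) adjusting for pre-treatment scores will also be used to analyze changes in" adolescents' outcomes, and "The magnitudes of changes in outcomes variables over time will be assessed using the paired t-test or Wilcoxon signed-rank test for continuous variables". These two sentences do not name the C-SSRS, but they too work on change in scores.

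Item (3) of the same section handles other outcomes person by person: "The percentage of adolescents who meet relapse criteria, and associated 95% confidence interval will be calculated", and likewise for recovery. Nothing equivalent is planned for suicidality, and section 7 has no safety-analysis part.

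The Statistical Methodology entry of the Study Summary describes the repeated measures ANOVA for CDRS-R, SAS-SR and CGAS. SAS-SR stands there where 7.2 has C-SSRS.

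**The concern.** For a safety endpoint on suicidality the question is how many adolescents developed it, or got worse, while on study treatment. Section 8.4 itself cites the FDA advisory on suicidal thinking and attempts in youth taking SSRIs, and some participants start fluoxetine or have a dose increase during continuation. An average of changes does not answer that question, because a fall in one adolescent offsets a rise in another.

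The stated time span adds to this. Change is taken over acute and continuation treatment together, and sections 4.1 and 4.3 admit only adolescents whose CGI-I showed improvement in the acute phase. If suicidality fell along with overall status, that fall is part of the contrast. It could mask a rise after week 16.

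The trial could then report no change, or improvement, on its primary suicidality endpoint without giving the number of adolescents who worsened.

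**Working it through.** **Inputs.** From the documents: n = 30 (section 7.1: "an intent-to-treat sample size of 30 was selected"); entry to continuation at week 16, with evaluations at weeks 24 and 32 (section 3.1). Assumed: all individual shifts below. The documents give no C-SSRS distribution and do not say which C-SSRS score would be analysed. The sample size was chosen for feasibility without an effect size or power, so there is no figure of the plan's own to reproduce.

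**Formulas.** Mean change = (sum of individual changes)/30. Its 95% CI is mean ± 2.045 × SD/√30 (t, 29 df). For x adolescents with new or worse suicidality, the exact (Clopper-Pearson) limits are the 2.5% quantile of Beta(x, 31 − x) and the 97.5% quantile of Beta(x + 1, 30 − x).

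**Main example, changes from week 16 to week 32.** Four go from 2 to 0, two from 0 to 4, and 24 do not change.
- Sum = 4 × (−2) + 2 × 4 = 0, so mean change = 0.0.
- Sum of squares = 4 × 4 + 2 × 16 = 48; SD = √(48/29) = 1.29; SE = 1.29/√30 = 0.235; 95% CI −0.48 to 0.48; paired t p = 1.0.
- Signed ranks: the four falls share rank 2.5 (total 10) and the two rises share rank 5.5 (total 11), so the Wilcoxon test is almost exactly balanced as well.
- Incidence: 2/30 = 6.7%, exact 95% CI 0.8% to 22.1%.

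**Other assumed patterns.**

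| Worsen | Improve | Mean change (95% CI) | t-test p | Incidence (exact 95% CI) |
|---|---|---|---|---|
| 0 | 0 | 0.00 | not defined | 0/30 = 0% (0 to 11.6%) |
| 3 by 1 point | 3 by 1 | 0.00 (−0.17 to 0.17) | 1.00 | 3/30 = 10.0% (2.1 to 26.5%) |
| 3 by 4 points | 6 by 2 | 0.00 (−0.59 to 0.59) | 1.00 | 3/30 = 10.0% (2.1 to 26.5%) |
| 3 by 1 point | 9 by 1 | −0.20 (−0.43 to 0.03) | 0.08 | 3/30 = 10.0% (2.1 to 26.5%) |

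A mean change of zero is thus compatible with an incidence of 0%, 6.7% or 10%. In the last row the mean points towards benefit although 10% worsened.

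**Time span.** For each adolescent, total change = acute change + continuation change. An ANOVA or mixed model with several time points could isolate weeks 16 to 32, but 7.2 does not name that contrast, and it would still be a difference of means.

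**Do other planned summaries supply the count?** Relapse in 7.2 requires five or more depressive symptoms on the K-SADS-PL, so an adolescent can have new suicidal ideation without counting as a relapse. Sections 8.1, 8.2 and 8.5.1 require adverse events to be recorded and reviewed annually, but set no tabulation or estimate.

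**The case against.** The strongest reply is that suicidality is watched closely. A symptom that develops or worsens is an adverse event (8.1), and all adverse events are recorded (8.2). The C-SSRS is used at medication visits and therapists assess suicidality at each session. Attempts, and serious ideation with refusal to contract for safety, go to an independent safety monitor (8.4). Outcome and adverse event data are reviewed yearly (8.5.1). This stands. A reader might infer that adolescents who become suicidal would go unseen; the documents do not support that. What is missing is a defined study-level statistic.

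Secondly, C-SSRS in 7.2 may be a slip for SAS-SR. The Study Summary has SAS-SR in that place, Hypothesis 6 concerns depressive symptoms and social and global functioning, and section 3.3 lists SAS-SR, not C-SSRS, as a secondary endpoint. Against that, C-SSRS appears twice in item (1), and 7.2 lists SAS-SR separately under secondary analyses. The documents do not settle it. If it is a slip, the objection removes the wrong method but leaves the endpoint with no analysis.

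Thirdly, this is an open-label pilot with feasibility as its primary outcome, and no stopping decision rests on the C-SSRS mean. That limits the consequence. But the plan already gives percentages with confidence intervals for consent, dropout, recovery and relapse, and a proportion with its interval needs no power.

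**Conclusion.** The point holds for the study-level result. As written, section 7 produces no figure for how many adolescents had new or worse suicidality during continuation treatment, although 3.4 makes suicidality a primary safety endpoint. With 30 adolescents, two such cases (6.7%, 0.8% to 22.1%) can coincide with a mean change of exactly zero. Even no cases would be informative, since the exact upper limit is then 11.6%.

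Two stronger readings should be avoided. One is that emergence will be cancelled: it can be, depending on how many adolescents start with suicidality that resolves, and the documents give no such number. The other is that any rise measured from before acute treatment is a continuation-phase event: it may have occurred before week 16, so only change from week 16 answers the question.

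The size rests on the assumed shifts. The conclusion that a mean change does not identify the number who worsened does not.

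**What to change.** 1. Reconcile the Study Summary with 7.2 on whether C-SSRS or SAS-SR belongs in the repeated measures ANOVA.
2. Remove C-SSRS from the continuous outcomes in 7.2, item (1). Report instead the number and percentage, with exact 95% CI, of adolescents with any suicidal behaviour, or ideation worse than at week 16, during weeks 16 to 32. State which C-SSRS items define each. This assumes a week 16 C-SSRS is available; section 3.1 shows a week 16 assessment.
3. Count cases from all sources already collected: the week 24 and 32 evaluations, visit-level C-SSRS, therapist assessments, AE/SAE records and safety-monitor records. The scheduled evaluations alone are not enough. Under 4.4.1 an adolescent may be removed following safety review of an attempt or serious ideation, and under 4.4.2 later evaluations depend on the family's permission. State how many adolescents lack a week 24 or 32 evaluation.
4. Add a case listing showing fluoxetine exposure. Any split by exposure should be descriptive only, because the groups are small and allocated by CGI-I response, not randomised (5.3).

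The cost is SAP wording, one table and the listing, with no new data. Using all sources gives fuller ascertainment in adolescents with more visits, so the count from weeks 24 and 32 alone should be shown beside it. The reported safety figure may look less favourable than a mean change.
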